### **9.4 Study Design:**

Describe study design in one to two sentences (e.g., prospective, use of existing records/data /specimens, observational, cross-sectional, interventional, randomized, placebo-controlled, cohort, etc.). Specify the phase – Phase I, II, III, or IV – for FDA-regulated investigational drug research

Randomized clinical trial comparing ASP, long, and pyonex needles by recruiting and treating 13 patients per group with the goal of analyzing at least 10 patients' questionnaires per group comparatively for effect and tolerance of different BFA needles.

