##### **Treatment Visit (Day 0) (may be the same day as screening visit):**

- Subjects will complete the Defense and Veterans Pain Rating Scale (DVPRS) and DVPRS Supplemental Questionnaire before treatment.
- Subjects will be prescribed naproxen 220 mg BID (twice a day) #15 as standard of care treatment for pain (unless they refuse or have a contraindication for use)
- Subjects will be given treatment according to their randomization group following the Acupuncture Procedure below: Step 1: Either the left or right ear is chosen for the placement of the needles per provider or patient preference. Step 2: Needles will be placed in the following points on the chosen ear: Cingulate Gyrus, Thalmus, Omega 2, Point Zero, and Shen Men. Step 3: If the patients desires further pain reduction, acupuncture needles will be placed in the same points in the opposite ear. The maximum number of needles in each ear is 5.

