# 11.0

## Statistical/Data Analysis Plan

### 11.1 Statistical Considerations:

List the statistical methods to be used to address the primary and secondary objectives, specific aims, and/or research hypotheses. Explain how missing data and outliers will be handled in the analysis. The analysis plan should be consistent with the study objectives. Include any sub-group analyses (e.g., gender or age group). Specify statistical methods and variables for each analysis. Describe how confounding variables will be controlled in the data analysis

**Outcome Measures:** There are two outcome measures. The effectiveness outcome measure is the Defense and Veterans Pain Rating Scale (DVPRS). The DVPRS [1,2] consists of an 11-point numerical rating scale with 0 indicating no pain and 10 indicating severe pain. It has been confirmed for reliability and validity in measuring both acute and chronic pain, and is currently the standard for pain measurement throughout DoD and VA health systems. The DVPRS demonstrates linear scale qualities allowing parametric methods to be used. There will be four repeated measurements of the DVPRS: pre-acupuncture, post-acupuncture, 24 hours and one week post-therapy. The needle tolerance outcome will be measured using an in-house developed questionnaire. It employs 5-point ordinal scales to evaluate 12 post-therapy experiences or perception encompassing adverse outcomes, inconveniences, and satisfaction. There will be three repeated measurements: post-acupuncture, 24 hours and 1 week post-therapy.

**Missing Data and Outliers:** Outliers will be checked for clerical error. If improperly recorded, the data will be corrected, and, if found to be properly recorded, will be retained. Medians, means and ranges will be calculated and assessed to accommodate extreme observations. Subjects with missing data will be excluded from analysis and the estimated sample size seen below adjusted for this eventuality. Furthermore, an analysis of sample characteristics of retained and dropped subjects will be performed to determine whether bias has been introduced due to exclusion.

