**Sub-group Analysis:** Analysis will center on differences between the three needle groups. The three treatment groups will allow inferences to be made as to whether each group is statistically different from one another. Medication is a potential confounder, but will be addressed by standardizing the dosage of analgesics used by all subjects rather than as a variable in a general linear model with the needle group variable.

Null Hypotheses:

H01 — there is no difference in means of the DVPRS between needle groups; and

H02 — there is no difference in means of the DVPRS between repeated measures; and

H03 — there is no difference in the distribution of the tolerance ordinal scales between needle groups.

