## 11.6 Data Analysis Plan: Complete description: Background, Objectives, Design, Step by Step how the project is going to be done, Data analysis plan:

Sample and needle group means, standard deviations, medians, interquartile ranges (IQR) and ranges will be calculated for interval variables. Frequency distributions will be produced for nominal and ordinal variables.

The null hypotheses H01 and H02 for the DVPRS outcome measure will be tested by a mixed effects repeated measures analysis of variance (rANOVA). In the event a null hypothesis is rejected, contrasts will be used to investigate effects and differences between and within research and time groups. Null hypotheses H03 will be tested with Chi Squared or Fisher's Exact tests. The significance level of multiple comparison tests will be corrected to  $\alpha = .05$  by the Holm method. [6]

[name], Senior Research Biostatistician Subject Matter Expert for Clinical Research Management under contracts OMNI 0004 3-82 and OMNI 0005 3-126, is the statistical consultant supporting this study. Statistical analysis will be performed with R Version 3.5.1. [7]

[6] Holm, S. 1979. A simple sequential rejective multiple test procedure. Scand. J. Statistics, 6: 65-70.

[7] R Core Team. R: A language and environment for statistical computing. R Foundation for Statistical Computing, Vienna, Austria. 2016 URL <http://www.R-project.org/>.

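### H02 tests change over time, which cannot be credited to needling, and its rejection opens within-arm contrasts that the wording would let stand in for a comparison of needles

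*Combined protocol and SAP*

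**What the plan says.** Section 11.1 names the DVPRS as the effectiveness measure and fixes its schedule: "There will be four repeated measurements of the DVPRS: pre-acupuncture, post-acupuncture, 24 hours and one week post-therapy". Two nulls concern it. H01 is that "there is no difference in means of the DVPRS between needle groups". H02 is that "there is no difference in means of the DVPRS between repeated measures".

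Section 9.4 describes a "Randomized clinical trial comparing ASP, long, and pyonex needles by recruiting and treating 13 patients per group". No sham or untreated arm appears there or in the list of groups in 10.1. At the Day 0 visit in 10.1, "Subjects will be prescribed naproxen 220 mg BID (twice a day) #15 as standard of care treatment for pain", with exceptions for refusal or contraindication.

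Section 11.6 tests H01 and H02 in one mixed-effects repeated-measures ANOVA and continues: "In the event a null hypothesis is rejected, contrasts will be used to investigate effects and differences between and within research and time groups". Multiple comparisons are Holm-corrected to 0.05, but the family of contrasts is not defined. No group-by-time hypothesis and no baseline-adjusted comparison is listed. Section 9.3 makes it a goal to begin identifying the most efficacious needle, and predicts that pyonex is best.

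**The concern.** A fall in DVPRS from before to after treatment mixes needling with naproxen, natural recovery and regression to the mean in people enrolled because they had pain. Without an untreated arm these cannot be separated. H02 is nonetheless a formal test on the effectiveness measure, and a common fall in all arms makes its rejection likely.

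Once H02 is rejected, 11.6 allows tests of change within each needle arm. With about 10 subjects per arm, each such test has modest power, so one arm will often reach significance while another does not, even when the needles are identical. Given the goal of finding the best needle, that pattern invites the reading that one needle works and another does not.

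The listed hypotheses offer little to set against it. H01 compares arm means over all four measures, including the one taken before any needle is placed. If a needle lowered every post-treatment score by 1.1 points, H01 would see only 3/4 × 1.1 = 0.825.

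**Working it through.** **Inputs from the documents.** Mean 4.4 and SD 2.4 (11.5); clinically important difference 25% of 4.4 = 1.1 points (11.5); 10 analysed per arm, 30 in total (11.2); four measurements, one before treatment (11.1); Holm to 0.05 (11.6).

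**Assumptions, not in the documents.** Within-subject correlation ρ of 0.3, 0.5 or 0.7 with compound symmetry; a common fall δ of 1.1 or 0.55 points, the same at all three post-treatment times; identical needles; H02 tested at 0.05.

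**Step 1: the plan's own power figure.** Sections 11.2 and 11.5 state power 0.44 at alpha 0.14. Take the between-groups repeated-measures F test with f = (1.1/2.4)/2 = 0.229, N = 30, m = 4 and ρ = 0.5:

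λ = f²·N·m / (1 + (m−1)ρ) = 0.0525 × 120 / 2.5 = 2.52, on 2 and 27 df.

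Power is 0.442, so 0.44 reproduces as a between-needle figure. At alpha 0.05 the same calculation gives 0.25.

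**Step 2: how often H02 rejects when the needles are identical.** With one baseline and three equal post-treatment means, the squared deviations of the time means sum to 0.75δ². Then

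λ = N × 0.75δ² / (SD²(1−ρ)), on 3 and 81 df.

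For δ = 1.1 and ρ = 0.5: 30 × 0.75 × 1.21 / (5.76 × 0.5) = 27.225 / 2.88 = 9.45, and power is 0.71. For ρ = 0.3 and 0.7 it is 0.55 and 0.92.

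**Step 3: why the arms disagree.** A stand-alone paired t-test in one arm of 10 has power p of 0.20, 0.25 and 0.39 for δ = 1.1 (ρ = 0.3, 0.5, 0.7). Three independent arms disagree with probability 1 − p³ − (1−p)³. At ρ = 0.5, p = 0.254, which gives 1 − 0.016 − 0.415 = 0.57. This is only the intuition; step 4 follows the planned sequence.

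**Step 4: the planned sequence by simulation.** 20,000 trials per setting: fit the repeated-measures ANOVA, require H02 to reject, then test baseline to 24 hours within each arm using the pooled error term. The last three columns give the share of all trials in which H02 rejects and one or two arms, but not all three, are significant.

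| Common fall | ρ | H02 rejects | Disagree, unadjusted | Disagree, Holm over 3 arms | Disagree, Holm over 9 contrasts |
|---|---|---|---|---|---|
| 1.1 | 0.3 | 55% | 39% | 25% | 15% |
| 1.1 | 0.5 | 71% | 53% | 36% | 23% |
| 1.1 | 0.7 | 92% | 70% | 54% | 43% |
| 0.55 | 0.3 | 16% | 9% | 5% | 3% |
| 0.55 | 0.5 | 21% | 13% | 8% | 4% |
| 0.55 | 0.7 | 34% | 22% | 13% | 7% |

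Repeat runs differ by up to about one percentage point.

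**Step 5: direct comparison of needles.** In the same simulated trials, the three pairwise between-arm contrasts of 24-hour change, with Holm, find a false difference in about 4%. Counting only trials in which H02 also rejects, the figure is about 3% to 4% at a fall of 1.1 and lower at 0.55.

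**The case against.** The strongest reply is that the plan never says needles will be ranked by which arm is significant. Section 11.1 centres the analysis on differences between the three groups, H01 is a between-needle test, and a time effect is a routine term in this ANOVA. Section 11.6 can also be read conventionally, with each rejected effect followed by contrasts for that effect alone. This stands in part: the misuse is allowed, not prescribed. But the sentence does not tie each contrast to its own null, and nothing rules out the within-arm route.

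A second reply is that Holm protects the comparisons. For between-needle contrasts it does. A reader might infer that letting H02 open them inflates false needle differences; step 5 shows that it does not. For within-arm contrasts Holm controls error against no change in that arm, not against no difference between arms, so it reduces disagreement without removing it.

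A third reply concerns naproxen. A reader might infer that it biases the comparison of needles. The documents do not support that: it is prescribed in every arm, 11.1 acknowledges medication as a possible confounder, and the time of the first dose is not given, so its share of the 10–15 minute change is unknown. It matters here only because it is one of several reasons why a change over time cannot be credited to needling.

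Finally, this is a pilot, and its aims compare needles without claiming benefit over no treatment. That limits the weight of the point. But the pilot is meant to inform a larger trial, so a mistaken ranking could carry forward.

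**Conclusion.** The point holds as a weakness in what the plan permits. Rejecting H02 says nothing about which needle is better and cannot be attributed to acupuncture in this design. The wording of 11.6 then opens within-arm contrasts, while no test of differential change between needles is listed.

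With identical needles, 10 per arm, SD 2.4 and a common 1.1-point fall, H02 rejects in about 55% to 92% of trials. H02 rejects with the arms disagreeing at 24 hours, after Holm over three arms, in about 25% to 54%. At a 0.55-point fall the latter is about 5% to 13%. These sizes rest on an assumed fall and an assumed correlation of 0.3 to 0.7, and they depend on the Holm family, which the plan leaves open.

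Two stronger conclusions are not supported: that the plan intends to rank needles by within-arm p-values, and that it treats H02 as proof that acupuncture works. The change is worth making because it costs only wording.

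**What to change.** In 11.1 and 11.6, label H02 and all within-arm changes as descriptive. Report them by arm with confidence intervals, and state that no inference on effectiveness or on the ranking of needles will be drawn from them.

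Base needle comparisons only on between-arm contrasts of baseline-adjusted post-treatment DVPRS, or on the group-by-time effect and its contrasts. Name the time point or points, define the Holm family, and give confidence intervals. These contrasts need not depend on rejection of H01, since Holm controls their error by itself.

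No subjects, visits or data are added. The sponsor gives up the H02 and within-arm p-values as formal results. The comparison that remains is imprecise, and the report should say so: at 10 per arm the approximate 95% half-width for a pairwise difference in change is 1.96 × √(4 × 2.4² × (1−ρ)/10), or 2.5, 2.1 and 1.6 points for ρ = 0.3, 0.5 and 0.7, against a target of 1.1.

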## 11.2 Sample Size:

A priori power analysis was performed using the DVPRS variable as described below. The analysis indicates a minimum of 10 subjects in each needle group, for a total sample size of 30, will have a power of 0.44 to detect the minimal clinically important difference at alpha = 0.14. We will be recruiting a total of 39 subjects, which is inclusive of a 30% drop out rate to accommodate those that may be lost to the study or have missing data to achieve a final total of 30 subjects.

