##### **Goals**

1) Begin to identify which of 3 needles is most efficacious for BFA treatment of pain; 2) Identify patient experiences and tolerance of three commonly used acupuncture needles at Mike O'Callaghan Military Medical Center at Nellis Air Force Base. This study will compare 30 patients (10 per needling group) and will serve as a pilot study for a potential larger randomized control trial (RCT) across multiple MTFs in the Defense Health Agency (DHA) to establish better BFA care practices. We will be recruiting a total of 39 subjects, which is inclusive of a 30% drop out rate to accommodate those that may be lost to the study or have missing data to achieve a final total of 30 subjects.

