## 11.3 Total number of subjects requested (including records and specimens):

39

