## 11.5 Please provide a justification for your sample size

The study is organized as a mixed effects, randomized design with repeated measures. Subject, gender and age are random effects as subjects are presumed to be a random representation of the population of adult male and female patients seeking treatment for this ailment and obtaining similar care at this and other Air Force medical treatment facilities. Time of repeated measure is a fixed effect as the pre- and post-therapy times cannot be generalized to other times. Needle group is a fixed effect as the needle employed cannot be generalized to other needles and conditions.

A priori power was assessed using G\*Power Version 3.1.9.3 using the DVPRS for effect size. [4] DVPRS mean (SD) pain intensity for a broad sample consisting of inpatients and outpatients suffering from acute and chronic pain has been found to be 4.4 (2.4). The minimal clinically important difference of an 11-point pain scale in patients as will be included in this study has been determined to be a 25% percent change in the score. [5] This difference, mean and SD were used for the DVPRS effect size.

A priori power analysis of the DVPRS variable using the statistical method described below indicates 10 subjects in each research group, for a total sample size of 30, will have a power of 0.44 to detect the minimal clinically important difference at alpha = 0.14.

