**13.6 Withdrawal from Study Participation:**

Explain the process for withdrawal and specify whether or not the subjects will be given the opportunity to withdraw their data their data/specimens in the event they wish to withdraw from the study

If a participant first agrees to participate and then changes their mind, they are free to withdraw consent and discontinue participation at any time. Their decision will not affect their ability to receive medical care and will not be penalized or lose any benefits to which they would otherwise be entitled. There are no risks from withdrawing. They will be advised in the Informed Consent process that if they decide to withdraw from the study early, we will ask them to discuss their decision with the study staff. The researcher may withdraw them from the study prior to the study's end without their consent for one or more of the following reasons: Failure to follow the instructions of the researchers and study staff. The

researcher decides that continuing their participation is not in their best interests. The study is cancelled. Other administrative reasons. Unanticipated circumstances. They become Pregnant. If they lose their status as a military health care beneficiary, they can no longer be included in the study.

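### Recruiting 39 with a 30% dropout rate leaves about 27 subjects, not 30; 39 covers a loss of only about 23%

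*Combined protocol and SAP*

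**What the plan says.** Section 11.2 gives the recruitment figure: "We will be recruiting a total of 39 subjects, which is inclusive of a 30% drop out rate". Section 9.3 (Goals) has the same sentence and ends it "to achieve a final total of 30 subjects". Both sections say the allowance is for subjects lost to the study and for subjects with missing data.

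Other sections depend on these figures or repeat them:

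- Section 11.1, on missing data: "Subjects with missing data will be excluded from analysis and the estimated sample size seen below adjusted for this eventuality". Every incomplete subject therefore reduces the analysed number, and the plan points to the sample-size section for the remedy.
- Section 11.2, on what is needed: "The analysis indicates a minimum of 10 subjects in each needle group".
- Section 11.5, on what that number provides: "10 subjects in each research group, for a total sample size of 30, will have a power of 0.44", at alpha = 0.14.
- Section 11.3 sets the total requested at 39.
- Sections 10.1 and 11.4 allocate by simple randomisation, with approximately 13 per arm.
- Section 9.4 recruits 13 per group "with the goal of analyzing at least 10" in each, and gives no dropout rate.
- Section 13.6 tells participants that "they are free to withdraw consent and discontinue participation at any time". It does not mention replacement.

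**The concern.** A dropout rate is a share of the people enrolled. Read that way, the recruitment sentence contradicts itself: 39 recruited, 30% lost and 30 remaining are three figures of which any two fix the third, and the three given do not agree. The pattern suggests a familiar slip, in which the target is multiplied by one plus the dropout rate when it should be divided by one minus the rate.

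At stake is whether the 30 analysed subjects, on which the stated power is conditional, can be expected at the plan's own dropout rate. Complete-case exclusion makes this matter more than it would under an analysis that used partial data. A subject must supply four pain ratings, and three tolerance questionnaires for the tolerance outcome. No section provides for replacing those who are lost. The study is also meant to prepare for a possible larger trial, where the same method of inflation would fall short again if it were carried over.

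**Working it through.** **Inputs**

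- Target analysed: 30 in total, 10 per arm (sections 9.3, 11.2, 11.5).
- Recruited: 39 in total, about 13 per arm (sections 9.3, 9.4, 11.2, 11.3, 11.4).
- Dropout: 30% (sections 9.3, 11.2).
- Power 0.44 at alpha = 0.14 with 30 analysed (sections 11.2, 11.5).
- Mean 4.4, SD 2.4, and a minimal clinically important difference of 25% (section 11.5), so 0.25 × 4.4 = 1.1 points.

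**Step 1: reproduce the plan's 39.** Target × (1 + dropout) = 30 × 1.30 = 39; per arm, 10 × 1.30 = 13. This is an exact match. The form that leaves the target after the loss is target / (1 − dropout) = 30 / 0.70 = 42.9, so 43; per arm, 10 / 0.70 = 14.3, so 15, or 45 in total. It does not give 39.

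**Step 2: what 39 delivers.**

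- Expected to remain at 30% loss: 39 × 0.70 = 27.3, or 9.1 per arm.
- Largest loss that still leaves 30: (39 − 30) / 39 = 9/39 = 23.1%.

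**Step 3: chance of keeping at least 30.** The number remaining is taken as binomial, with each recruit lost independently.

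| Recruited | Loss | Expected to remain | P(at least 30 remain) |
|---|---|---|---|
| 39 | 30% | 27.3 | 0.22 |
| 39 | 23.1% | 30.0 | 0.59 |
| 43 | 30% | 30.1 | 0.59 |
| 45 | 30% | 31.5 | 0.75 |

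**Step 4: chance that every arm keeps at least 10.** This assumes simple randomisation with probability 1/3 per arm and loss independent of arm (multinomial). The result is 0.02 for 39 recruits at 30% loss, 0.08 for 39 at 23.1%, 0.095 for 43 at 30% and 0.16 for 45 at 30%. With no loss at all, 39 recruits give only 0.66. These low values therefore come largely from simple randomisation and from planning for exactly 30 in expectation. The slip itself accounts only for the difference between 0.095 and 0.02.

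**Step 5: effect on power.** The documents do not give the effect size f or the correlation entered in G*Power, so I avoided assuming them. I solved for the noncentrality that gives power 0.44 at N = 30 and alpha = 0.14, multiplied it by 27/30 = 0.90, and recomputed the power with the degrees of freedom for N = 27.

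| Test | Degrees of freedom | Power at N = 30 | Power at N = 27 |
|---|---|---|---|
| Between groups | 2, N − 3 | 0.44 | 0.411 |
| Time | 3, 3(N − 3) | 0.44 | 0.411 |
| Group by time | 6, 3(N − 3) | 0.44 | 0.409 |

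**Step 6: cross-check with assumed inputs.** Take f = (1.1 / 2.4) / 2 = 0.229, four measurements and an assumed correlation of 0.5. The between-group noncentrality is f² × N × 4 / (1 + 3 × 0.5). Power is 0.442 at N = 30, which agrees with the plan's 0.44, and 0.412 at N = 27. With f = 0.216 (one arm differs by 1.1) or f = 0.187 (three evenly spaced means with range 1.1), and correlations from 0.3 to 0.7, the drop ranges from 1.8 to 3.5 percentage points.

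**The case against.** The best defence is that 39 is exactly 30 × 1.30, and 13 is exactly 10 × 1.30. The 30% may have been meant as an over-recruitment margin on the target and loosely labelled. Then 39 and 30 are both intended, only the label is wrong, and 27 is nobody's forecast. That may well be how the number arose. But the text calls it a dropout rate that the 39 already includes, and no section defines it as a share of completers. The sentence would need the same correction on this reading too.

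Second, the consequence is slight. This is an openly low-powered pilot, and about 3 points from 0.44 changes nothing it will decide. That stands, and it is why the point is minor.

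Third, other features of the plan limit loss. Baseline, treatment and the first post-treatment assessment fall in one visit (section 10.1). Follow-up lasts 7 days, has time windows, and can be done in person, by telephone or online. This is fair: true loss may be below 30%, and the recruitment margin is not the only thing that helps. It remains the only numerical allowance, though, and the plan chose 30%.

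Fourth, the per-arm probabilities reflect simple randomisation more than the slip. That also stands; they bear on how firmly 10 per group can be promised, and the arithmetic finding does not rest on them. Likewise, section 13.6 is silent on replacement and does not forbid it, and repetition of the slip in a later trial is a possibility that the documents do not establish.

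**Conclusion.** The recruitment sentence in sections 9.3 and 11.2 is wrong as written. At the stated 30% dropout, 39 recruits leave about 27, a shortfall of about 3 subjects; 39 is enough only for a loss of up to 9 (23.1%). This is arithmetic and needs no assumption beyond reading the dropout rate as a share of those recruited.

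The 0.22 chance of keeping at least 30 assumes independent losses at exactly 30%. The fall in power from 0.44 to about 0.41 takes the plan's 0.44 as given and does not depend on the unreported G*Power inputs. The power statement in section 11.5 is conditional on 30 analysed and is not in dispute, and section 9.4 contains no error on this point. The error is minor but certain, it appears twice, and it is worth correcting because the exclusion rule in section 11.1 leans on it.

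**What to change.** In sections 9.3 and 11.2, keep two of the three figures and correct the third.

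- **(a) Keep 39 and 30.** State that 39 allows for the loss or exclusion of 9 subjects, about 23%. This changes one sentence in each section and adds no patients.
- **(b) Keep 39 and 30%.** State that about 27 subjects, about 9 per arm, are expected. In section 11.2, add that power would then be about 3 percentage points below 0.44, after re-running G*Power with the inputs used originally. This adds no patients, but it needs those inputs and sits awkwardly with the aim in section 9.4 of at least 10 analysed per group.
- **(c) Keep 30% and 30.** Recruit 43, or 45 for equal arms. This adds 4 to 6 patients, needs matching changes in sections 9.4, 10.1, 11.3 and 11.4, and recovers only about 3 points of power.

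Option (a) is the simplest and is enough for a pilot, as long as the team is content to plan on a loss of about 23%. If it believes 30% is realistic, (b) is the honest version.

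In section 11.2 it would also help to call 10 per group a target, in line with section 9.4, since neither 39 recruits nor simple randomisation secures it. That is a wording change only.
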